### **10.3.2 Reporting AEs**

NONSERIOUS AEs are to be reported on the AE CRFs.

### **10.3.3 Reporting SAEs**

Any SAE, regardless of causal relationship, will be reported to the Sponsor's Medical Monitor or CRO designee within 24 hours after the Investigator becomes aware of the SAE. Compliance with this time requirement is essential so that the Sponsor may comply with its regulatory obligations.

The initial SAE report should be completed as fully as possible but will contain, at a minimum items number 1 to 6:

1. Subject number/ID, sex, and age/date of birth
2. The date of report
3. Name of the reporter
4. Name of the suspected medicinal product
5. A description of the event, including event term(s), seriousness criteria, and a clinical summary of the event
6. Causality assessment

If the causality assessment is not provided in the initial report an updated report with the causality must be provided within 24 hours, once assessed.

Information about all SAEs (either initial or follow-up information) will be collected and recorded in English on the electronic SAE Report Form within the EDC system. The Investigator will assess the relationship to each specific component of the study treatment. If the event meets serious criteria and it is not possible to access the EDC system, a paper SAE Report Form will be sent to the CRO via email or fax, or the Investigator will call the CRO SAE hotline

within 24 hours of being made aware of the SAE (reference the site manual for contact information). When the EDC system becomes available again, the SAE information will be entered within 24 hours of the system becoming available.

The Investigator will report follow-up information relating to an SAE to the Sponsor's Medical Monitor or CRO designee within 24 hours of awareness updating the electronic CRF with the new information or by submitting a paper SAE Report Form in the event that the EDC is not available. When the EDC system becomes available, the SAE information will be entered within 24 hours. The subject will be observed and monitored carefully until the condition resolves or stabilizes.

All deaths are to be thoroughly investigated and reported. Autopsy reports and death certificates are to be obtained, if possible.

The Sponsor and/or its designee are responsible for reporting SAEs to all applicable regulatory agencies and the central ethics committees within the required timeline.

The Investigators are responsible for submitting required safety information to their local IRB as per local regulations. This information includes, but is not limited to, any safety alert letter received from the Sponsor and any SAEs occurring at their study site.

#### **10.3.4 Relationship to Study Drug**

The causal relationship of the AE to study drug (vadadustat or epoetin alfa) will be assessed by both the Investigator and the Sponsor.

The assessment of causal relationship to study drug will be evidence-based, and not based on the premise that all AEs are possibly causally related to study drug until proven otherwise.

Examples of evidence that would suggest a causal relationship between the study drug and the AE include the occurrence of an AE that is uncommon and known to be strongly associated with drug exposure (e.g., angioedema, hepatic injury, and Stevens-Johnson syndrome) or an AE that is uncommon in the population exposed to the drug.

The causal relationship of the AE is assessed using a binary system, and AEs are classified as either 'related' or 'unrelated';

**Related:** There is 'reasonable possibility' that the drug caused the AE. The AE follows a reasonable temporal sequence from the time of drug administration. There is supportive evidence (facts) to suggest a possible causal relationship, irrespective of the degree of certainty between the observed AE and the drug.

**Unrelated:** An AE does not follow a reasonable temporal sequence from administration of the product and/or there is no reasonable possibility that the drug caused the AE. This assessment includes situations where the AE is related to other factors such as the subject's clinical state, other therapeutic interventions, or concomitant drugs administered to the subject.

Default assessments using the 'related' category without supportive evidence for a causal relationship to study drug are generally uninformative and do not contribute meaningfully to the development of the safety profile of the drug or to subject protection.

Investigators are encouraged to choose the most plausible cause for the event(s) from the following list: medical history, lack of efficacy/worsening of treated condition, study treatment,

other treatment (concomitant, or previous), withdrawal of study treatment, administration error, protocol-related procedure, others (specify).

#### **10.3.5 Severity**

The Investigator will assess each AE as either MILD, MODERATE, or SEVERE using the following guidelines to describe the maximum severity of the AE:

MILD: Does not interfere with subject's usual function

MODERATE: Interferes to some extent with subject's usual function

SEVERE: Interferes significantly with subject's usual function

Note that a **severe** AE is not necessarily a **serious** AE. For example, a headache may be severe in intensity, but would not be classified as serious unless it met 1 of the criteria for serious events listed above.

#### **10.3.6 Follow-up of Unresolved Events**

All AEs will be followed until they are resolved or the Investigator assesses them as chronic or stable or the subject's participation in the trial ends (i.e., until a final report is completed for that subject).

In addition, all SAEs and those nonserious events assessed by the Investigator as related to the study drug will continue to be followed even after the subject's participation in the trial is over. Such events will be followed until they resolve or until the Investigator assesses them as "chronic" or "stable". Resolution of such events is to be documented on the appropriate CRF.

### **10.4 Exposure In-Utero**

A pregnancy in a female subject will be confirmed by a positive serum  $\beta$  human chorionic gonadotropin test.

The study drug will be immediately discontinued once the pregnancy of a female study participant has been confirmed.

If any study participant becomes or is found to be pregnant while receiving a study drug (vadadustat or epoetin alfa) or within 30 days of discontinuing the study drug, the pregnancy will be recorded on the Pregnancy Reporting Form/Exposure in Utero Form in EDC within 24 hours of awareness of the pregnancy or the Investigator will call the CRO SAE hotline within 24 hours of being made aware of the pregnancy.

Pregnancy during this time frame of the female partner of a male subject will also be reported.

The Pregnancy Reporting Form/Exposure in Utero Form will be completed with all known information regarding the pregnancy at the time of reporting. Study site personnel will update the form with additional information regarding the pregnancy and the outcome of the pregnancy as it becomes available until the outcome of the pregnancy is reported.

The Investigator will follow the subject (or female partner of a male subject) until completion of the pregnancy. If the outcome of the pregnancy meets the criteria for classification as an SAE (i.e., spontaneous abortion, stillbirth, neonatal death within 1 month of birth, or congenital

anomaly [including that in an aborted fetus]), the Investigator will also follow the procedures for reporting an SAE within 24 hours of awareness. A pregnancy in and of itself is not considered an AE; however, unexpected complications are considered AEs.

Additional information about pregnancy outcomes follows:

- Note that “spontaneous abortion” includes miscarriage and missed abortion.
- All neonatal deaths that occur within 1 month of birth will be reported, without regard to causality, as SAEs. In addition, any infant death after 1 month that the Investigator assesses as related or unrelated to the in utero exposure to the study drug will also be reported.
- In the case of a live birth, the “normality” of the newborn can be assessed at time of birth.
- The “normality” of an aborted fetus can be assessed by gross visual inspection unless there are pre-abortion laboratory findings suggestive of a congenital anomaly.

## 10.5 Special Situations

Certain safety events, called ‘Special Situations’, that occur in association with study drug may require reporting. These Special Situations include, but are not limited to, the following:

- Overdose of the medicinal product
  - Epoetin alfa overdose – The PI or SmPC will be referenced for information on epoetin alfa overdosing.
  - Vadarustat overdose – There is no known antidote for vadarustat. In cases of suspected overdose, subjects will be treated per standard medical practice based on the Investigator’s judgment and dose delays and reductions may be implemented as necessary.

Chronic overdosage with vadarustat may result in excessive production of red blood cells and polycythemia. Polycythemia can be potentially life threatening and may result in severe thrombosis and death (known as hyperviscosity syndrome). If hyperviscosity syndrome is observed, vadarustat will be discontinued and standard treatment for polycythemic hyperviscosity syndrome will be initiated (i.e., phlebotomy).

Dose-limiting toxicity in exploratory toxicology studies was due to hemoglobinuric nephropathy in the rat and emesis associated with body weight loss in the dog. In the rat, doses  $\geq 500$  mg/kg were not tolerated in two 7-day exploratory toxicology studies. The probable cause of the findings is considered to be intravascular hemolysis leading to hemoglobinuric nephropathy.

The clinical data from human volunteer subjects and renal study subjects demonstrate that currently there is no evidence of any drug-related hemolysis associated with vadarustat at the doses studied. The highest dose in the majority of subjects exposed to vadarustat was up to 600 mg daily with minimal exposures at doses higher than this (up to 1200 mg single dose and up to 900 mg daily for 10 days). No conclusion concerning the safety profile of vadarustat at doses higher than 600 mg daily can be drawn.

- Suspected abuse/misuse of the medicinal product
- Inadvertent or accidental exposure to the medicinal product
- Medication error involving the medicinal product (with or without subject exposure to the Sponsor's medicinal product [e.g., name confusion])
- Drug-drug interaction.

Special situations will be reported on the Special Situations CRF whether they result in an AE/SAE or not. Special situations with associated AE/SAE will also be reported on the corresponding AE/SAE forms, following applicable AE or SAE process.

## **10.6 Safety Monitoring**

This is an open label study allowing the study team full access to safety data which will be reviewed on a regular basis, throughout the course of the study. Safety monitoring will be performed as described in the Medical Monitor Plan.

## 11 DATA ANALYSIS

Data collected throughout the study will be summarized using descriptive statistics and listed in the by-subject listings. Continuous variables will be summarized using number of subjects with mean, standard deviation (SD), median, minimum, and maximum. For categorical variables, the number and percentage of subjects in each category will be tabulated. Summaries will be provided by treatment group within appropriate analysis populations (as defined in Section 11.2, Study Analysis Populations) and by time point/time period, as appropriate.

### 11.1 Sample Size Estimation

Approximately 95 subjects are planned for enrollment in the Main study with 40 and 55 subjects randomized to the low epoetin alfa dose group and the high epoetin alfa dose group, respectively. Approximately 30 subjects are planned for enrollment in the ESA hyporesponder parallel study.

Sample size reflects the exploratory nature of this study.

Enrollment may be increased by up to 20 additional subjects in the Main study and by up to 30 additional subjects in the ESA hyporesponder parallel study to ensure adequate data is captured for the primary, PK/PD, and safety endpoints.

### 11.2 Study Analysis Populations

The following analysis populations will be used in this study:

- Randomized population: defined as all randomized subjects. Analyses of this population will be based on the randomized treatment.
- Full Analysis Population (FAS): all subjects in the randomized population who received at least one dose of study drug and had at least one Hb assessment during the primary efficacy evaluation period. Analyses of this population will be based on the randomized treatment.
- Safety Population: all subjects in the randomized population who received at least one dose of study treatment. Analysis of this population will be based on the actual treatment received. Subjects who received in error some vadadustat and some epoetin alfa will be classified by the more frequently received drug.
- Per protocol (PP) population: all randomized subjects who received study drug during the primary evaluation period, had at least one Hb assessment during the primary efficacy evaluation period, received no rescue therapy (with ESA or transfusion) prior to the evaluation period, and had no major protocol deviation affecting the primary endpoint analyses. Major protocol deviations leading to exclusion from the PP population will be specified prior to database lock and recorded in a separate document. Analyses of this population will be based on actual treatment received.

Efficacy analyses will utilize the Randomized, Full Analysis, and PP Populations while safety analyses will utilize the Safety Population.

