### 5.3 Efficacy Endpoints

#### 5.3.1 Primary Endpoints

The primary endpoint will be the mean change in Hb between Baseline (average pretreatment Hb) and the primary evaluation period (average Hb from Weeks 10 to 12).

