### **7.6.2 Temporary Interruption of Study Drug**

Subjects who temporarily interrupt their study drug (vadadustat or epoetin alfa) after receiving the first dose and prior to completion of the study, will continue with the study visits, safety assessments, and other activities as deemed applicable through Week 20, and will complete the 4-week Safety Follow-Up Period and the Visit 15/Week 24 assessments (see [Appendix A](#): Schedule of Activities).

During the study, a subject may interrupt study drug (vadadustat or epoetin alfa) for any of the following reasons:

- AE
- Missed dialysis visit (epoetin alfa arm)
- Investigator's discretion
- Rapid rise in Hb (defined as  $>1.0$  g/dL in any 2-week period)
- Hb above 11.0 g/dL
- ESA use (vadadustat arm)

Unless contraindicated, treatment will be resumed whenever possible and assessed at every visit following study drug interruption.

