#### 8.4.6 Guidelines for Dose Adjustments

Dose adjustments will be guided by Hb concentrations and the Guidelines for Dose Adjustment (see below). Hb will be monitored via central laboratory throughout the study to determine if the dose of study drug (vadadustat or epoetin alfa) will be adjusted, interrupted, or maintained as follows:

- Dose adjustments are based on the Investigator's clinical discretion, incorporating the protocol guidance below as well as the subject's current Hb level, trajectory, and variability; symptoms; cardiovascular risk; and other features of his/her clinical condition(s).
- If a dose increase or decrease is required to achieve and maintain Hb levels within the target range of 10.0 to 11.0 g/dL, inclusive, dose is adjusted by 1 dose level (for vadadustat 1 tablet [150 mg], for epoetin alfa approximately 25%).
- In general, do not increase the dose more frequently than once every 4 weeks. A one-time dose increase after 2 weeks is allowed on only two occasions.
  - A subject's dose may be increased by 1 dose level if the subject has a decline in Hb  $\geq 0.5$  g/dL from Baseline/Day 1 in the first 2-week period (the initial period from Baseline/Day 1 to Week 2 following conversion from prior epoetin alfa therapy).
  - A subject's dose may also be increased by 1 dose level in the first 2-week period after initiation of TIW dosing (from Week 12 to Week 14) for subjects that meet criteria for transitioning from daily to TIW dosing.
- Reduce or interrupt the dose in the setting of a rapid rise in Hb (defined as  $>1.0$  g/dL in any 2-week period)
- Reduce or interrupt the dose in the setting of Hb  $>11.0$  g/dL
- Interrupt the dose in the setting of a Hb  $>12.0$  g/dL until Hb value falls below 11.0 g/dL. After Hb falls below 11.0 g/dL, restart study drug and consider restarting at a lower dose.

**Note:** The minimum dose of vadadustat will be 150 mg daily or TIW (1 tablet daily/TIW) and the maximum dose will be 900 mg daily or TIW (6 tablets daily/TIW).

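### The per-protocol exposure rule for Weeks 10 to 12 has no exception for protocol-directed high-Hb interruptions, so a compliant subject held through the window is excluded because Hb was high

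*Protocol*

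**What the plan says.** Section 5.3.1 defines the window as "the primary evaluation period (average Hb from Weeks 10 to 12"). Appendix A schedules Weeks 10, 11 and 12 on Days 71, 78 and 85.

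Section 11.2 defines PP as "all randomized subjects who received study drug during the primary evaluation period, had at least one Hb assessment" in that window, without ESA or transfusion rescue beforehand and without a major deviation affecting the primary endpoint. The list of major deviations is left to a later document; the exposure criterion is fixed here. The Full Analysis Population (FAS) asks only that a subject "received at least one dose of study drug and had at least one Hb assessment during the primary efficacy evaluation period". PP is a named efficacy population: "Efficacy analyses will utilize the Randomized, Full Analysis, and PP Populations while safety analyses will utilize the Safety Population".

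Section 8.4.6 applies to both arms. Above 12.0 g/dL, dosing stops "until Hb value falls below 11.0 g/dL. After Hb falls below 11.0 g/dL, restart study drug". Above 11.0 g/dL, or after a rise of more than 1.0 g/dL in two weeks, the dose is either reduced or interrupted. Section 7.6.2 lists Hb above 11.0 g/dL and rapid rise among the reasons for temporary interruption, and says such subjects "will continue with the study visits, safety assessments, and other activities as deemed applicable through Week 20".

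**The concern.** A per-protocol set should keep those who were treated as the protocol directs. Here the exposure clause and the interruption rule pull against each other. A subject whose Hb is high enough to be held across the whole window, and who attends every visit, has no deviation and has usable endpoint data, but received no drug in the window and so is out. The trigger for exclusion is a high Hb, and Hb is the endpoint.

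At stake are two PP results: the mean Hb change to Weeks 10 to 12 (the primary endpoint) and the proportion within 10.0 to 11.0 g/dL (a key secondary endpoint). Removing subjects who are above range shrinks the denominator of the second without touching its numerator, and lowers the first.

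**Working it through.** The protocol gives no figure to reproduce. The check is a reading of the text, followed by an illustration of feasibility and size.

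**Text.** Take a subject held from the Week 8 result until after Week 12.

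- Randomized population: in.
- FAS: in, with at least one dose at some time and Hb in the window.
- Major-deviation clause: passed, because the hold is directed by 8.4.6.
- PP exposure clause: failed, because no drug was received in Weeks 10 to 12. Section 11.2 states no exception.

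**Can a hold last that long?** The protocol gives no rate of fall off drug, so the rate r is assumed to lie between 0.25 and 1.0 g/dL per week. Days from the Week 8 value h to 11.0 g/dL = 7 × (h − 11.0) / r.

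| Hb at Week 8 | r = 0.25 | r = 0.5 | r = 0.75 | r = 1.0 |
|---|---|---|---|---|
| 12.1 | 30.8 | 15.4 | 10.3 | 7.7 |
| 12.5 | 42.0 | 21.0 | 14.0 | 10.5 |
| 13.0 | 56.0 | 28.0 | 18.7 | 14.0 |

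Week 8 is Day 57. Using scheduled visits only, the hold covers the window if Hb is not yet below 11.0 g/dL on Day 78, that is if the time is at least 78 − 57 = 21 days. If Hb first drops below 11.0 g/dL in the Week 12 sample, the restart comes as the window closes or later. Five of the twelve cells meet the condition, one of them exactly at the boundary. From 12.5 g/dL the limit is r = (12.5 − 11.0)/3 = 0.5 g/dL per week. A full-window hold is plausible at slower falls and does not occur at faster ones.

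**Size.** Arm sizes follow from Sections 8.4.1 and 11.1: 40 at 3:3:2 gives 15/15/10; 55 at 3:3:3:2 gives 15/15/15/10; 30 at 1:1 gives 15/15. Suppose k of n subjects are dropped and their mean change exceeds that of the rest by g. The arm mean then moves by −k × g / n. With g assumed between 1.0 and 2.5 g/dL and k of 1 or 2:

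- n = 15: from −1 × 1.0/15 = −0.07 to −2 × 2.5/15 = −0.33 g/dL.
- n = 10: from −1 × 1.0/10 = −0.10 to −2 × 2.5/10 = −0.50 g/dL.

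For the in-range proportion, assume none of the dropped subjects is in range. Then 8/15 (53.3%) becomes 8/14 (57.1%) for one dropped and 8/13 (61.5%) for two.

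**Direction.** The rescue clause removes mainly low-Hb subjects, since 8.4.9.2 generally reserves ESA rescue for Hb below 8.5 g/dL. That pushes the PP mean up, against the effect above. For the in-range proportion the two exclusions work the same way, because each tends to remove out-of-range subjects.

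**The case against.** Several points on the other side stand.

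- The trigger is narrow. Only Hb above 12.0 g/dL calls for interruption outright, and all adjustments are subject to investigator discretion. Subjects whose dose was reduced stay in PP. So does anyone who took a single dose in the window, if received means any dose.
- The protocol's own background points to few cases: Section 4.3 reports few excursions above range, and Section 6.3 a prompt fall in mean Hb after stopping. Section 8.4.3 allows extra Hb tests, which could bring a restart forward.
- Requiring exposure in the window is a recognised on-treatment definition, and the FAS stands beside it.

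A reader might go further and infer that the rule hides overshoot, or spoils the comparison of starting doses. The documents do not support that. The FAS and Randomized populations keep these subjects. Hb above 12.0, 13.0 and 14.0 g/dL and rapid rises are safety endpoints (Section 5.5), tabulated by treatment group (Section 11.7). Reasons for exclusion from each population are listed by subject (Section 11.4). More overshoot at higher starting doses is an expectation only: no overshoot by arm is given, and doses are titrated well before Week 10. Nor is a downward bias in the PP mean established, given the rescue exclusion. No error rate is affected, since the analyses are descriptive.

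What these points do not remove is that an efficacy population labelled per protocol excludes some subjects for a course the protocol itself directs.

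**Conclusion.** The point holds, as a minor one. In the protocol version whose Section 11.2 is available, PP drops a compliant subject held throughout Weeks 10 to 12 for high Hb. The effect is to raise the PP in-range proportion and to pull the PP mean change down, with the net effect on the mean uncertain. The distortion is confined to the descriptive PP efficacy results.

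The sizes shown rest on assumed rates of fall, assumed gaps from the arm mean, one or two subjects per arm, and dropped subjects being out of range. The number of such subjects is not given and is probably small.

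The file also contains a later protocol version, which adds a nephrectomy exclusion, a statin section and an amendment history. Its Section 8.4.6 carries the same interruption rule, but its Section 11.2 is not in the text available, so the point is verified for the earlier version only.

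**What to change.** Keep the exposure criterion in Section 11.2 and add one sentence: a subject whose study drug was interrupted during the primary evaluation period under Section 8.4.6, for Hb above 11.0 g/dL, Hb above 12.0 g/dL or a rapid rise, is treated as meeting the criterion and is not excluded from PP on that ground. Confirm whether Section 11.2 of the later version has the same wording, and amend it there if so.

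Replacing the criterion with absence of permanent discontinuation would be too broad. It would also admit subjects off drug for the whole window because of an adverse event or at the investigator's discretion.

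The cost is one sentence, with no new data: Hb and dosing are already recorded, though the reason for a hold must be identifiable when the population is assigned. The PP in-range figure may look slightly less favourable, and PP will contain a few subjects with no drug intake in the window. No change to the dosing rule is implied.
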